7.6 Exploratory Analyses

In exploratory analyses, we will compare the occurrence of AMI 1) in persons receiving HEPLISAV-B as their first vaccination against hepatitis B with persons receiving the comparator vaccine as their first vaccination against hepatitis B and 2) in persons receiving a first dose of HEPLISAV-B as their second or subsequent dose of hepatitis B vaccine with persons receiving the comparator vaccine as their second or subsequent dose of hepatitis B vaccine. The models will be stratified by vaccination history (initial vs. subsequent dose of hepatitis B vaccine) and alternatively, with vaccination as a covariate and/or effect modifier.

7.7 Model Selection Rationale

Potential confounders to include in multivariable models are listed in Section 6.3. These covariates will be assessed for their availability and ability for adjusting crude results, including an examination of their distributions and missingness. Bivariate associations of potential confounders with the outcome (AMI), exposure, and each other will be examined. For those with suggestions of imbalance with either exposure or outcome, the association between exposure and outcome will be stratified by categories of the potential confounder to look for differences across strata (potential effect modification) and influence on summary estimates of association (confounding). The variables will ultimately be selected based on a combination of the a priori decisions and a qualitative assessment of the empirical relationships. We will assess the robustness of cut-point selections and groupings and consider tightly confounded variables and their collinearity. Note that we will NOT use an algorithmic backward, forward or stepwise process, and that the results of the multivariable model should corroborate the knowledge gained during the model-building process.

7.8 Clustering

We will examine clustering within medical center in our data using a random effects model ^[34]. In our sample data based on members vaccinated in 2015, the intra-class correlation coefficient was extremely small (<.00001), which would result in a minimal impact on power. If there is

some evidence of clustering we will adjust for it in our final model using random medical center effects.

7.9 Power Analyses

Approximately 50,000 patients (HEPLISAV-B: 25,000; another hepatitis B vaccine: approximately 25,000) will be included in the study and the accrual is assumed to be uniform during a period of approximately 10.5 months. Each patient will be followed for up to 13 months after their first dose of HEPLISAV-B or comparator vaccine administered during the study vaccination period. A 10% loss to follow-up during the study with a uniform loss rate is assumed. Assuming no difference in the risk of AMI between the two groups, we anticipate approximately 41 events at 12 months, 68 events at 18 months, and 78 events at the end of study if the event rate is 1.5/1000 person-years. In the first interim analysis, the study will have approximately 83% power to detect a hazard ratio \geq 2.5 and 60% power to detect a HR \geq 2.0, and in the second interim analysis the study will have 81% power to detect a HR \geq 2.0. In the final analysis, the study will have approximately 87% power to exclude HR \geq 2.0. The anticipated number of events based on other event rates and the power for a non-inferiority test based on other non-inferiority margins for the final analysis is presented in Table 7-1.

Time, Months	Event rate per 1000 person- years	# Events	Power, HR = 2.0 alpha = 0.025	Power, HR = 2.5 alpha = 0.025	Power, HR = 3.0 alpha = 0.025	Power, HR = 3.5 alpha = 0.025	Power, HR = 4.0 alpha = 0.025
9	1.0	16	0.277	0.44	0.583	0.696	0.782
	1.5	23	0.388	0.601	0.757	0.858	0.918
	2.0	31	0.490	0.725	0.866	0.938	0.972
12	1.0	27	0.442	0.669	0.820	0.906	0.952
	1.5	41	0.603	0.836	0.941	0.980	0.994
	2.0	55	0.728	0.924	0.982	0.996	0.999
18	1.0	45	0.644	0.869	0.959	0.988	0.997
	1.5	68	0.814	0.965	0.995	0.999	1.000
	2.0	90	0.909	0.992	0.999	1.000	1.000
24	1.0	52	0.705	0.911	0.977	0.995	0.999
	1.5	78	0.865	0.982	0.998	1.000	1.000
	2.0	104	0.942	0.997	1.000	1.000	1.000

Table 7-1:	Power for a Non-inferiority Test to Reject a Hazard Ratio in a Cox
	Proportional Hazards Model

Assumptions:

- Final HEPLISAV-B medical centers will be the same 7 as initially planned or will result in the same number of vaccine recipients in each arm
- Only doses given in family practice and internal medicine will be included (90% of all adult hepatitis B vaccine doses)
- Essentially all doses in HEPLISAV-B medical centers in family practice and internal medicine will be HEPLISAV-B
- Accrual of both HEPLISAV-B and comparator vaccine is roughly evenly distributed through the year (primarily affects number of person-years of follow up at interim analysis)
- Total doses given annually during the study period will be ~30% fewer than the number given in 2015 (~15% decline seen from 2015 to 2016, lesser decline observed subsequently)
- 10% lost to follow-up rate during 13-month follow-up, assuming a uniform loss rate, giving an average of 1.02 person-years per recipient at the final analysis

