4.4 Study Period

The study will begin with administration of the first dose of HEPLISAV-B and is contingent upon ACIP and RIPC recommendation of HEPLISAV-B. The study vaccination period will occur until 25,000 patients have received at least 1 dose of HEPLISAV-B, expected to take approximately 10.5 months based on historical vaccination trends. Each patient will be followed until the earliest of disenrollment from KPSC (not due to death and allowing for a 31-day gap in membership), death from any cause, or the end of the 13-month follow-up period after the index dose given during the vaccination period.

Table 4-1:Adult Hepatitis B Vaccine Recipients: Active Member at First Dose
Date, 2015 by Target (HEPLISAV-B) and Comparator Medical
Centers

	8 Comparator	7 Target	Total
	Medical Centers	Medical Centers	
N	47,964	45,766	93,730
Age (years)			
Mean (SD)	49.1 (10.83)	49.0 (10.90)	49.1 (10.86)
Sex	n (%)	n (%)	n (%)
Female	23,229 (48.43)	22,400 (48.94)	45,629 (48.68)
Male	24,735 (51.57)	23,366 (51.06)	48,101 (51.32)
Race/Ethnicity	n (%)	n (%)	n (%)
Asian	4043 (8.43)	5810 (12.7)	9853 (10.51)
Black	4027 (8.4)	4742 (10.36)	8769 (9.36)
Multiple	242 (0.5)	190 (0.42)	432 (0.46)
Native Am/Alaskan	152 (0.32)	127 (0.28)	279 (0.3)
Others	340 (0.71)	432 (0.94)	772 (0.82)
Pacific Islander	728 (1.52)	691 (1.51)	1419 (1.51)
Unknown	1107 (2.31)	829 (1.81)	1936 (2.07)
White	14,482 (30.19)	7914 (17.29)	22,396 (23.89)
Hispanic	22,843 (47.63)	25,031 (54.69)	47,874 (51.08)
Had type 2 diabetes history prior to the first dose	n (%)	n (%)	n (%)
No	9851 (20.54)	10,094 (22.06)	19,945 (21.28)
Yes	38,113 (79.46)	35,672 (77.94)	73,785 (78.72)
Had AMI history between 01/01/2010 to first dose date	n (%)	n (%)	n (%)
No	47,359 (98.74)	45,260 (98.89)	92,619 (98.81)
Yes	605 (1.26)	506 (1.11)	1111 (1.19)
Had hospitalized AMI in 12 months after first dose date	n (%)	n (%)	n (%)
No	47,891 (99.85)	45,713 (99.88)	93,604 (99.87)
Yes	73 (0.15)	53 (0.12)	126 (0.13)

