6.2.3 Definition of primary AMI outcome

For the primary outcome, AMI will be defined as definite plus probable Type 1 AMI ^[31, 32]. A Type 1 AMI is due to a primary coronary event, such as plaque rupture, ulceration, fissuring, erosion, or dissection with resulting intraluminal thrombus in one or more of the coronary arteries leading to decreased myocardial blood flow or distal platelet emboli with ensuing myocyte necrosis. The patient may have underlying severe coronary artery disease (CAD) but on occasion non-obstructive or no CAD.

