6.5 Data Monitoring

An independent Data Monitoring Committee (DMC) will be established, comprised of a cardiovascular disease epidemiologist, a biostatistician familiar with vaccine post-licensure safety studies, and a vaccine safety expert. The committee members will be proposed and retained by KPSC. The DMC will review quarterly reports of vaccine accrual and aggregated number of unconfirmed AMI cases, and the interim and final analyses, as specified below.

The number of patients receiving any dose of hepatitis B vaccine and the aggregate number of unconfirmed AMIs will be compiled monthly to monitor assumptions used to determine study duration (vaccine uptake and AMI event rates). The number of vaccines will be identified by cluster and age strata (<50 years and \geq 50 years) and will be available beginning 3 months after the first HEPLISAV-B dose is administered. The number of AMI events will be aggregated across all medical centers and not by vaccine group, to avoid 'spending' type 1 error. As noted above, a 3-month lag period will be used to allow incorporation of claims data (Section 6.4), so the number of AMI events will first be available beginning 4 months after the first HEPLISAV-B dose (1 month of patient follow-up plus 3 months for data settling). After this 4-month period, KPSC will provide the reports to the sponsor monthly and to the DMC quarterly. These data will be used to monitor uptake and event rates that can be compared to the assumptions in the sample size calculation and help anticipate the need for extension of the study, if necessary. If HEPLISAV-B accrual is slower than anticipated or if observed AMI event rates are lower than

anticipated, the number of patients receiving HEPLISAV-B could be increased, along with an equivalent number of patients receiving comparator vaccine, by extending the study vaccination period.

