7.3 Primary Analysis

For the final analysis of the primary objective, we will use a non-inferiority framework to test the null hypothesis of increased risk of Type 1 AMI among HEPLISAV-B recipients versus comparator vaccine recipients. Based on anticipated number of confirmed events, the study will have approximately 87% power to exclude a hazard ratio of 2.0 or greater (Section 7.9), testing the hypothesis: H_0 : $HR \ge 2$, H_a : HR < 2.

The rates of occurrence of first Type 1 AMI event during the study period among HEPLISAV-B recipients and comparator vaccine recipients will be compared using a Cox proportional hazards regression model employing inverse probability of treatment weighting (IPTW)^[33]. The IPTW provides an assessment of the closeness of match in the weighted analysis across all variables, providing a sense of the degree of control of imbalance between the vaccine exposure groups. Two tables will be created comparing the cohort of HEPLISAV-B recipients to the cohort of recipients of the comparator vaccine. The first table will be unweighted, showing the true distribution of recipient characteristics. The second table will be weighted by the inverse probability of treatment as estimated by a propensity score model. Standardized difference scores will be used to assess whether balance of covariates is achieved between the cohorts. These 2 tables will show the effectiveness of the weighting at reducing effective differences between the cohorts.

The primary analysis will be conducted on confirmed Type 1 AMIs. Variables to consider in the propensity model are listed in Section 6.3. The primary exposure will be vaccine group

(HEPLISAV-B vs. comparator vaccine), and the outcome will be confirmed AMI. Clustering by medical center will be considered through random effects variables representing medical center. Censoring events will include end of study, disenrollment from Kaiser Foundation Health Plan (allowing for a 31-day gap in membership), and death from causes other than AMI. A hazard ratio of AMI for HEPLISAV-B versus the comparator vaccine, adjusted for potential confounding factors, and associated 95% confidence interval will be reported.

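### The 87% power is claimed for confirmed events, but one rate of 1.5 per 1000 person-years serves both the unconfirmed and the adjudicated outcome, with no allowance for confirmation

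*Protocol*

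**What the plan says.** Section 7.3 makes the power claim for the adjudicated outcome: "Based on anticipated number of confirmed events, the study will have approximately 87% power to exclude a hazard ratio of 2.0 or greater". Section 6.2.3 defines that outcome: "AMI will be defined as definite plus probable Type 1 AMI". Potential events come from any diagnosis position (sections 6.2.1 and 6.2.2).

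Section 7.9 gives the inputs: "Approximately 50,000 patients (HEPLISAV-B: 25,000; another hepatitis B vaccine: approximately 25,000) will be included in the study", and "Assuming no difference in the risk of AMI between the two groups". It then lists 41 events at 12 months, 68 at 18 months, "and 78 events at the end of study if the event rate is 1.5/1000 person-years". Section 7.1 defines the events behind the 41 and 68 differently, as unconfirmed Type 1 AMI coded as the principal discharge diagnosis.

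The only historical rate is in Table 4-1, in the row "Had hospitalized AMI in 12 months after first dose date": 126 of 93,730 recipients in 2015. The row states neither AMI type nor diagnosis position, and does not mention adjudication.

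On monitoring, section 6.5 says that "the aggregate number of unconfirmed AMIs will be compiled monthly to monitor assumptions used to determine study duration". It allows the vaccination period to be lengthened if accrual or AMI rates fall short.

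**The concern.** Two different outcomes share one rate. The interim outcome is unadjudicated and limited to the principal position; the final outcome is adjudicated and drawn from any position. Their rates agree only if secondary-position Type 1 events happen to replace the cases lost at adjudication, and the protocol neither says this nor gives a confirmation fraction.

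The protocol itself shows that losses are to be expected. Its code list includes Type 2 infarction (I21.A1). Section 4.3 reports that about 45% of persons with AMI were found through claims from outside facilities. Section 8.1 classes cases without the data needed for adjudication as undeterminable, and these do not enter the primary outcome.

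The study exists to exclude a doubling of AMI risk after a pre-licensure imbalance. If confirmed events fall short, it may end without an answer. The count meant to warn of this is a count of a different outcome.

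**Working it through.** **Inputs.** N = 50,000, 1:1; true HR 1.0; margin HR 2.0; one-sided alpha 0.025; 10% uniform loss over 13 months; 1.02 person-years per recipient (section 7.9 and its assumptions). 2015 events: 126 of 93,730 (Table 4-1).

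**1. The plan's own figure.** Person-years: 50,000 × 1.02 = 51,000, or 50,000 × (13/12) × 0.95 = 51,458. At 1.5 per 1000 this gives 76.5 to 77.2 events, against 78 stated. Power = Φ(½ × √D × ln 2 − 1.96). For D = 78: Φ(3.061 − 1.960) = Φ(1.101) = 0.8645, against 0.865 in Table 7-1. All twelve entries in the HR 2.0 column reproduce within 0.01. With uniform accrual over 10.5 months, the same 1.5 rate gives 40.8 events at 12 months and 68.9 at 18 months (stated: 41 and 68). One rate therefore drives the interim and final figures alike.

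**2. The 2015 rate.** 126/93,730 = 1.344 per 1000 persons over 12 months. Under the plan's loss rate, mean follow-up over 12 months is 1 − ½ × 0.10 × 12/13 = 0.954 years, so the rate is 1.344/0.954 = 1.409 per 1000 person-years. The exact Poisson 95% interval is 1.17 to 1.68, which contains 1.5.

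**3. Events and power at full confirmation.** 51,000 × 1.344/1000 = 68.5 (69.2 with 51,458); 51,000 × 1.409/1000 = 71.9 (72.5 with 51,458). Power is 0.82 to 0.84.

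**4. Effect of a confirmation share.** The documents give none, so the shares below are assumptions. A net share means confirmed Type 1 events in any position, divided by the events that the base rate counts. The 2015 columns use 51,000 person-years; the last two multiply 78 by the share.

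| Assumed net share | Events at 1.344–1.409 | Power | Events at 1.5 | Power |
|---|---|---|---|---|
| 100% | 68.5–71.9 | 0.82–0.84 | 78 | 0.865 |
| 90% | 61.7–64.7 | 0.78–0.80 | 70.2 | 0.83 |
| 80% | 54.8–57.5 | 0.73–0.75 | 62.4 | 0.78 |
| 70% | 48.0–50.3 | 0.67–0.69 | 54.6 | 0.73 |
| 60% | 41.1–43.1 | 0.60–0.62 | 46.8 | 0.66 |

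**5. Break-even.** Power of 80% needs 4 × (1.960 + 0.842)²/(ln 2)² = 65.3, so 66 events. That is 66/71.9 = 92% to 66/68.5 = 96% of the events expected at the 2015 rate, or 66/78 = 85% of those expected at 1.5.

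**6. What the monitored count can show.** If unconfirmed events run at 1.5 per 1000 and 80% are confirmed, the monthly count is on plan while confirmed events head for 62 instead of 78. A low unconfirmed rate would show; this loss would not.

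**The case against.** The calculation itself is right, and the dispute is about an input. A reader might infer that the 2015 data contradict 1.5. They do not: 1.5 lies inside the sampling interval, and the comparator centers alone had 73/47,964 = 1.52 per 1000 persons (target centers 53/45,766 = 1.16). The gap in the base rate alone costs about 3 to 5 points and leaves power above 80%.

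A reader might also take Table 4-1 as a count of AMI of every type. The label carries no restriction, but the protocol does not say which codes or positions were used. If it was principal position only, secondary-position Type 1 events would be gained at the final analysis and would offset part of the loss. The interim outcome, too, is already labelled Type 1, although unadjudicated.

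A third tempting reading is that power is known to be near 60-80%. That rests wholly on assumed shares. Section 7.9 also makes the 78 events conditional on the rate, and Table 7-1 prints a row at 1.0 per 1000 (52 events, power 0.705), so sensitivity to the rate is disclosed.

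Finally, one might conclude that monitoring would miss any shortfall until the end. A low base rate would appear in the monthly counts. Section 7.1 adds conditional power at both interims, without saying whether those AMI events are confirmed, and lets the DMC recommend extension. Nothing says that adjudication waits for the end of the study.

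All of this stands. It limits the size of the point, but does not explain how a power claim for confirmed events follows from a rate also used for unconfirmed ones.

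**Conclusion.** The concern holds as a mismatch between the power claim and its input. Section 7.3 promises 87% for confirmed events; section 7.9 supports it with a rate of unstated origin that is applied unchanged to unconfirmed interim events and adjudicated final events. On the protocol's only historical rate, 82-84% is the figure at full confirmation, from about 69 to 73 events. Below full net confirmation, power falls; holding 80% at that rate needs 92-96% of events confirmed as Type 1. How far it falls cannot be determined from the protocol, and the illustrative 60-80% depends on assumed net shares of 60-90%. Routine monitoring under section 6.5 detects a low base rate, but not losses at adjudication or to other AMI types.

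**What to change.** State where 1.5 per 1000 person-years comes from: codes, diagnosis position, AMI type, and whether events were adjudicated. Restate sections 7.3 and 7.9 and Table 7-1 for confirmed Type 1 events, using the 2015 rate times an explicit, justified confirmation fraction, net of any secondary-position gains, with a sensitivity range. Show 82-84% as the figure at full confirmation. Keep the interim event counts on their own, unconfirmed basis.

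In section 6.5, add the pooled, group-masked number of adjudicated Type 1 events, or unconfirmed events times the running confirmation fraction, to the counts used to decide on extending the vaccination period. Pooled counts involve no comparison between groups, so they spend no type 1 error.

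The cost is a less favourable stated power, and adjudication on a rolling basis if that is not already intended. The fix itself requires no extra patients. One limit should be acknowledged: if vaccination closes at 10.5 months, the 3-month lag leaves data to month 7.5. Ignoring losses, that is 50,000 × 7.5/10.5 = 35,714 recipients with a mean of 3.75 months each, or 11,161 person-years and about 17 unconfirmed events at 1.5. A running fraction from so few events is imprecise, so the fraction justified in advance matters most.

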8.0 DATA MANAGEMENT

8.1 Data Processing

Electronic health record data are extracted and maintained securely in the electronic RDW database at KPSC. The database is regularly supported with appropriate backup and recovery options. Only authorized study personnel with passwords can access the database.

Data processing in this study will be performed by programmers and analysts at KPSC using SAS (version 9.3 or higher; SAS Institute, Cary, NC). No imputation for missing data will be performed. We expect there to be a very low rate of missing data in the electronic health records. Potential AMI cases missing data required for adjudication will be reported as possible/unable to determine. Any loss to follow-up due to leaving the KPSC health plan (Section 7.3) will be addressed in data analysis by the truncation of person-time in the event rate calculations.

8.2 Data Quality

Quality control of data will include range and consistency checks for all study variables, with additional consistency checks for hepatitis B vaccine exposure. For example, discordant records (eg, vaccine name with wrong manufacturer or invalid lot number), HEPLISAV-B administrations in non-target medical centers, and comparator vaccine administrations in target medical centers will trigger a review of the medical records. For the planned adjudication of the

AMI events, we will rely on proven methods for obtaining necessary medical records, assembling the records into a secure PDF file for review, and storage and tracking. Potential AMI events will be individually adjudicated by 2 trained cardiologist reviewers masked to vaccine exposure using a standardized form, with a third cardiologist to review cases with disagreement (Section 6.2). An online event adjudication system will be used for collection of data elements and final adjudication decisions; appropriate, automated quality checks will be employed for ensuring complete data entry, correct skip patterns, and answer range/values. Double programming will be conducted for assignment of the cohort (vaccine group) and outcome (AMI), and all source code will be reviewed by a second analyst.

9.0 **REGULATORY AND ETHICAL CONSIDERATIONS**

The protocol will be reviewed and approved by the KPSC Institutional Review Board (IRB). All study staff with access to protected health information are trained in procedures to protect the confidentiality of subject data. Informed consent is not needed for HEPLISAV-B vaccination, as the vaccine will be approved by the U.S. FDA and recommended for eligible KPSC members as part of routine clinical care. Individual written Health Insurance Portability and Accountability Act (HIPAA) authorizations will not be required prior to initiating data collection using electronic health records. Patients who are suspected to have been treated for AMI outside the KPSC system and have incomplete records at KPSC may be contacted to obtain HIPAA authorization to request a copy of their health records from outside facilities for the AMI episode. Adverse event reporting is not required, as this is a non-interventional study based on secondary use of KPSC electronic health records. Adverse events cannot be identified spontaneously under the current methodology, so there will not be individual reporting of adverse events. The study will be conducted in accordance with the protocol, applicable regulatory requirements, and good pharmacoepidemiologic practice.

REFERENCES

- 1. CDC. *Viral Hepatitis Surveillance United States*, 2015. 2015; Available from: https://www.cdc.gov/hepatitis/statistics/2015surveillance/pdfs/2015HepSurveillanc eRpt.pdf.
- Mast, E.E., et al., A comprehensive immunization strategy to eliminate transmission of hepatitis B virus infection in the United States: recommendations of the Advisory Committee on Immunization Practices (ACIP) Part II: immunization of adults. MMWR Recomm Rep, 2006. 55(RR-16): p. 1-33; quiz CE1-4.
- 3. Abara, W.E., et al., *Hepatitis B Vaccination, Screening, and Linkage to Care: Best Practice Advice From the American College of Physicians and the Centers for Disease Control and Prevention.* Ann Intern Med, 2017. **167**(11): p. 794-804.
- 4. Centers for Disease, C. and Prevention, *Use of hepatitis B vaccination for adults with diabetes mellitus: recommendations of the Advisory Committee on Immunization Practices (ACIP).* MMWR Morb Mortal Wkly Rep, 2011. **60**(50): p. 1709-11.
- 5. *HEPLISAV-B Package Insert*. Available from: http://www.dynavax.com/files/7815/1026/3335/HEPLISAV-B-Package-Insert.pdf.
